Effects of Ivabradine on residual myocardial ischemia after PCI evaluated by stress echocardiography.

Protocol Version 2.1

Date 15/09/2015

NCT number: not available

Investigators: [name]*, [name]*, [name]*, [name]*, [name]*, [name]*, [name]*, [name] PhD* and [name]*.

*Cardiovascular, Respiratory, Geriatric, Anesthesiologic and Nephrologic Sciences Department, Umberto I Hospital, Sapienza University of Rome, Italy.

INTRODUCTION

Stable angina is a syndrome characterized by a transitory condition of acute myocardial ischemic attacks caused by an imbalance between myocardial perfusion and metabolic demand [1]. The antianginal drugs and the percutaneous coronary revascularization, are essential to treat the persistent symptoms. However, in some cases, when small vessels or side branches are significantly involved with hard or impossible reperfusion, drug therapy is the only strategy to prevent the worsening of ischemic heart disease and to reduce the symptoms. Heart rate is the major determinant of cardiac output and myocardial oxygen consumption, therefore the reduction of heart rate in patients with stable angina can be considered a goal of the therapy [2]. Ivabradine is an antianginal agent that specifically inhibits the pacemaker (If) current, resulting in selective HR reduction with no negative effects on blood pressure and inotropism [3]. In patients with chronic heart failure, Ivabradine improves clinical outcomes if used with beta-blockers under well documented efficacy and safety [4].

In previous studies, Ivabradine reduced anginal symptomatology but has not clearly demonstrated improvements of the outcomes in patients with chronic ischemic disease without left-ventricular systolic dysfunction [5-7]. More recently, in CONTROL-2 Study, in patients with stable angina, the combination of the two therapies ivabradine and β -blockers together demonstrated good tolerability, safety, and also pronounced clinical improvements, compared to β -blockers up titration [8]. Moreover, an interesting SHIFT substudy showed the reversed LV remodeling with marked reductions of LV volumes and significant improvements of LV ejection fraction (LVEF) in patients treated with Ivabradine [9].

In this context, in order to define the role of Ivabradine in patients with residual angina after PCI, we aimed to quantify the clinical benefits of adding ivabradine to standard antischemic therapy, in symptomatic patients for residual myocardial ischemia after PCI, using more precise indicators of oxygen consumption.

Furthermore, we studied the effects of ivabradine on diastolic function (both at rest and after exercise) and on the ventricular remodeling.

METHODS.

We investigated the efficacy of treatments with Ivabradine in addition to full anti-ischemic therapy (as per guidelines) compared with the latter alone in patients with signs or symptoms of residual angina underwent percutaneous coronary intervention plus stent implantation. The main purpose was to evaluate if addition of ivabradine to standard therapy might increase the threshold for angina improving the stress tolerance and exercise duration in terms of double product (DP) and triple product (TP), respectively calculated as a product between HR and systolic blood pressure and the product between DP and ejection time. In our opinion these, indirectly, reflect the true myocardial oxygen consumption (MVO₂) and the improvement of mechanical load that the ventricle can withstand at different levels of exercise. Triple product is closely related to the tension-time index, a measure of ventricular work and oxygen demand that is found by multiplying the average pressure in the ventricle during the period in which it ejects blood by the time it takes to do this [10].

The second objective was to evaluate changes at rest and after the stress test of diastolic function and ventricular remodeling, using echocardiographic parameters.

Study Population

In this randomized, prospective, single-center study, all the patients selected were with chronic coronary artery disease undergoing percutaneous coronary intervention (PCI) plus stent implantation, residual angina and on treatment with full anti-ischemic therapy with and without Ivabradine. In all patients, revascularization was complete as far as possible, all coronary lesions resulting in a stenosis greater than 50% in vessels of a caliber greater than two millimeters were treated. The inclusion criteria was: coronary artery disease with chronic stable angina for more than three months (Canadian Cardiovascular Society–CCS-class I-III); percutaneous revascularization with stent implantation at least one; signs/symptoms of residual ischemia; sinus rhythm; HR \geq 70 bpm at rest; ability to perform an echocardiogram stress test with the tilting bicycle stress test (BST); good acoustic window; age \geq 18 years. The main exclusion criteria were: drugs intolerance or hypersensitivity, EF \leq 40 % with NYHA class III to IV; CCS IV; atrial fibrillation or flutter; presence of a pacemaker or implantable defibrillator; II or III degree AV block; HR \leq 70 bpm at rest or sick sinus syndrome; any condition that could interfere with the ability to exercise stress test like Wolff- Parkinson-White syndrome, left bundle branch block, left ventricular hypertrophy; rate-corrected QT interval (QTc) greater than 500 ms or the use of drugs that prolong the QTc interval; symptomatic hypotension or uncontrolled hypertension (systolic blood pressure at rest \geq 180 mmHg or diastolic blood pressure \geq 100 mmHg); severe liver disease and severe renal impairment (creatinine clearance \leq 30 ml/min); electrolyte disorders; uncontrolled thyroid disease and pregnancy. All patients signed informed consent prior to randomization. The study was designed according to the principles outlined in the Declaration of Helsinki and was approved by the Ethics Committee and Institutional Review.

Study design and Treatment

All patients with CCS I-III angina, were considered and only patients who met the inclusion criteria, after signing the informed consent form, were included in our study. The treatment was assigned on the basis of a 1:1 ratio to receive Ivabradine 5 mg twice daily (Ivabradine Group, IG) or standard therapy according to the guidelines (Control Group, CG). Both therapeutic strategies were titrated to the maximum tolerated dose, in particular β -blockers. All patients were submitted to clinical evaluation and exercise stress echocardiography at enrollment time (T1) and after 30 days of therapy (T2). During the period between exercise stress tests, clinical evaluation with ivabradine therapy up-titration was performed after 15 days.

Patient evaluation included physical examination, HR measurement by 12-lead electrocardiograms (ECG), two-dimensional, Doppler and Tissue Doppler echocardiography, using Philips iE33 system (Andover, Massachusetts, USA) and a supine bicycle ergometer stress test. During the test, operators recorded echocardiograms before and during the exercise. The parameters measured were: left ventricular (LV) 2D diameters, systolic function parameters, ejection time, LV end-systolic and end-diastolic volumes in relation to body surface area (end-diastolic and end-systolic indices [EDI and ESI]), and LV ejection fraction (LVEF) were assessed according to Simpson's method (as suggested by the American Society of Echocardiography and European Association of Echocardiography) [11].

Bicycle Stress Test. Exercise test, was performed using a semi-recumbent and tilting bicycle ergometer (X-SCRIBE EKG Analysis, Mortara Instruments; Ergometrics 800s, Ergoline West-Germany) with an initial workload set at 25 Watt and increments of 25Watt/ 2 min. HR and rhythm is continuously recorded using a 12-lead electrocardiogram, blood pressure was measured at baseline, at peak exercise, and during the last minute of each stage including recovery.

The rate of exercise, which was measured in metabolic equivalents (1 metabolic equivalent = 3.6 ml/kg/min), and the duration of exercise were assessed as well.

Chronotropic reserve was estimated using the formula: $100 \times (\text{peak HR} - \text{resting HR}) / (220 - \text{age}) - \text{resting HR}$.

Stress test was interrupted if the patient developed chest pain, ST segment elevation > 0.1 mV at 80 ms from the J point, or a significant adverse event (significant ventricular arrhythmia, limiting breathlessness, dizziness, muscular exhaustion, chest pain, arterial pressure drop ≥ 10 mmHg with symptoms, or severe systemic hypertension).

Echocardiography. Images were acquired in standard views and displayed side by side in a quad-screen format. All images were digitally recorded in continuous-loop format. Total work at the ischemic threshold and peak exercise were calculated. Double product (DP) was calculated during the last stage of exercise performed by multiplying maximum systolic BP by maximum HR; triple product (TP), was obtained integrating DP with ejection time (ET) measured with mitral annular PW-TDI (BP x SBP x ET).

In addition diastolic function was evaluated by PW Doppler E and A waves, TDI derived E' measurements and E/E' ratio. Mitral annular E' velocity was estimated as the average between lateral and septal velocity.

Drugs with possible interactions with ivabradine such as non-dihydropyridine calcium channel blockers, class I antiarrhythmics and strong inhibitors of cytochrome P450 3A4, were not allowed, whereas short-acting nitrates were allowed up to 3 hours before exercise or after exercise if needed. At the end of the tests, double, triple products and diastolic function evaluation, were collected by a blind operator.

All parameters recorded and calculated in off-line analysis were included in our register.

Statistical analysis.

The sample size was not calculated because it was a pilot study. Continuous variables were presented as mean \pm standard deviation (SD) and categorical variables as percentages. Categorical variables were compared among groups using the chi-square test or Fisher's exact test when appropriate, whereas continuous variables were compared with Student t-test. All tests were two-sided and a *p* value less than 0.05 was considered statistically significant. All analyses were performed using SPSS software, version 20.0 for Windows.

COMPLIANCE WITH ETHICAL STANDARDS

All authors declare that they have no conflict of interests. No funding was received for this study.

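### The second objective names ventricular remodeling, but one on-treatment echo at 30 days cannot separate a structural change from the effect of a lower heart rate

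*Combined protocol and SAP*

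**What the plan says.** The last paragraph of the Introduction announces a study of ivabradine's effect on diastolic function "and on the ventricular remodeling". Methods repeats this as the second aim: "The second objective was to evaluate changes at rest and after the stress test of diastolic function and ventricular remodeling". The sentence goes on to say that echocardiographic parameters will be used, but it does not name the ones that represent remodeling.

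Study design and Treatment lists the measurements. They include "LV end-systolic and end-diastolic volumes in relation to body surface area" (EDI and ESI), LV diameters, and "LV ejection fraction (LVEF) were assessed according to Simpson's method". Patients had "exercise stress echocardiography at enrollment time (T1) and after 30 days of therapy (T2"), and in between, "clinical evaluation with ivabradine therapy up-titration was performed after 15 days". No other echo visit is described.

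The Introduction shows what the authors have in mind. It says that a substudy of a heart-failure trial "showed the reversed LV remodeling with marked reductions of LV volumes and significant improvements of LV ejection fraction (LVEF"). It also describes ivabradine as selectively lowering heart rate.

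Statistical analysis compares continuous variables between groups with Student's t-test. It gives no covariates and no rule for interpreting the LV measures.

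**The concern.** In its usual sense, remodeling is a change in the structure of the ventricle. Volumes and LVEF are indirect evidence of it, because they also depend on the loading and rate at which the image is taken. The T2 image is taken on a drug whose stated action is to slow the heart, so the two arms are expected to be imaged at different rates. Randomization does not remove this difference, because the difference in rate is itself an effect of the assigned treatment.

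What is at stake is the conclusion that the second objective permits. A fall in ESI with a rise in LVEF would resemble the favourable pattern described in the Introduction. A rise in EDI could be taken for dilatation. A null result could be taken as absence of a remodeling effect. The design supports none of these three readings as a statement about structure.

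**Working it through.** **Timing.** Up-titration is at day 15 and T2 at day 30: 30 − 15 = 15 days. T2 is the last measurement and is taken on therapy.

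**Plan's own figure.** There is none to reproduce. Statistical analysis gives no sample size, and no target change in volumes or LVEF is stated.

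**Can rate alone move the named measures?** The inputs below are assumptions, not figures from the documents, except that 75 bpm is compatible with the entry requirement of at least 70 bpm at rest (Study Population).

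- Resting heart rate falls from 75 to 65 bpm.
- Baseline EDI is 70 and ESI 30 ml/m2, so the stroke volume index is 70 − 30 = 40 and LVEF is 40/70 = 57.1%.
- Resting cardiac output is constant, so stroke volume scales with the inverse of rate.

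New stroke volume index = 40 × 75/65 = 46.15, a rise of 15.4%. LVEF is stroke volume index divided by EDI.

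| Case at 65 bpm | EDI | ESI | LVEF |
|---|---|---|---|
| ESI fixed | 30 + 46.15 = 76.2 | 30 | 46.15/76.15 = 60.6% (+3.5 points) |
| EDI fixed | 70 | 70 − 46.15 = 23.8 (−20.5%) | 46.15/70 = 65.9% (+8.8 points) |
| Half compensation, ESI fixed | 30 + 43.08 = 73.1 | 30 | 43.08/73.08 = 58.9% (+1.8 points) |
| No compensation | 70 | 30 | 57.1% (0) |

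In the half-compensation row the stroke volume index is 40 + 6.15/2 = 43.08.

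**Sensitivity.** Take full compensation, a baseline rate of 70 to 80 bpm, a fall of 5 to 15 bpm and a baseline LVEF of 50% to 60%. The rise in LVEF then runs from about 1.5 points (80 bpm, fall of 5, LVEF 60%, ESI fixed: 61.5%) to about 16 points (70 bpm, fall of 15, LVEF 60%, EDI fixed: 76.4%).

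**From one arm to the between-arm contrast.** The table shows a before-after change in one arm. It equals the between-arm difference only if control-arm heart rate does not change. Study design and Treatment says that therapy is titrated in both arms, beta-blockers in particular, so control-arm rate may fall too. Suppose it falls by 5 bpm, to 70, with ESI fixed: stroke volume index = 40 × 75/70 = 42.86, EDI = 72.86 and LVEF = 42.86/72.86 = 58.8%. The between-arm differences are then 76.15 − 72.86 = 3.3 ml/m2 in EDI and 60.6 − 58.8 = 1.8 points in LVEF. With an equal fall in both arms, they are 0.

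**The case against.** The randomized on-treatment contrast is a valid estimate of the total effect of adding ivabradine, and lowering the rate is how the drug works. The objective is expressly tied to echocardiographic parameters, and the Introduction uses reversed remodeling to mean smaller volumes and higher LVEF. On that reading, remodeling is only a label for those measures, and the comparison can be made. The trial is a pilot, the objective is secondary, every input to the illustration is assumed, and its range includes zero.

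Most of this stands, and it limits the point. What remains is that the label claims more than the comparison can show, and that nothing in the plan restricts the claim.

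A reader might also infer several stronger things that the documents do not support:

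- *That the second objective cannot be answered.* Diastolic function is untouched by this argument, and 30-day changes in EDI, ESI and LVEF can be compared.
- *That 30 days is too short for remodeling to occur.* The documents give no time course. The supportable statement is that this design cannot distinguish it.
- *That this population has little to reverse.* The exclusion is "EF \leq 40 % with NYHA class III to IV", a conjunction. Patients with low EF in a lower NYHA class remain eligible, and nothing is said about baseline volumes.
- *That a rate effect would be reported as remodeling.* The plan has no interpretation rule either way, so this would be a prediction.
- *That a rise in EDI and LVEF with unchanged ESI identifies a rate effect.* The EDI-fixed case shows that rate can equally lower ESI and raise LVEF, which is closer to the pattern described as reverse remodeling.

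**Conclusion.** The point holds as a limit on interpretation. With one on-treatment echo at 30 days and no off-drug, later or rate-matched reading, a group difference in EDI, ESI or LVEF cannot be attributed to structure rather than rate, and a null result cannot be read as absence of remodeling.

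The size is uncertain. On the main set of assumed inputs, rate alone gives 0 to 8.8 LVEF points in one arm, depending on how far stroke volume compensates and which volume absorbs it. The between-arm figure is smaller if control-arm rate also falls. The conclusion does not depend on any one of these values. It rests on three things: remodeling taken in its structural sense, a heart-rate difference between arms at T2, and at least partial compensation by stroke volume.

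This is an inexpensive improvement to a secondary objective. The main objective on double and triple product is not affected.

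**What to change.** Restate this part of the second objective as the between-group difference in 30-day, on-treatment change in LV volumes (EDI, ESI) and LVEF. Keep diastolic function as a separate item. State that no conclusion on structural remodeling will be drawn in either direction, and make the matching change to the aim at the end of the Introduction.

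Report heart rate at each echo acquisition, by arm, beside EDI, ESI and LVEF. This shows how far the arms differed in rate when imaged; it does not by itself separate the two explanations. Do not use a fixed EDI/ESI pattern to label a change as a rate effect. Any analysis adjusted for heart rate should be called exploratory, because heart rate at T2 is measured after randomization and is affected by treatment.

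The data are already collected: ECG heart rate and the LV measures are part of the existing evaluation. No visit, procedure or treatment changes. The cost is some rewording, one added line in the results tables, and a less ambitious secondary claim.

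### Does a resting heart rate of exactly 70 bpm, which meets both an inclusion and an exclusion criterion, call for a change to the plan?

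*Combined protocol and SAP*

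**What the plan says.** The Study Population section gives the two lists in one paragraph. The inclusion list asks for "HR \geq 70 bpm at rest". The exclusion list names "HR \leq 70 bpm at rest or sick sinus syndrome". Study design and Treatment adds that "only patients who met the inclusion criteria, after signing the informed consent form, were included in our study". That sentence refers to the inclusion list alone and does not rank the two lists. The same section provides for "HR measurement by 12-lead electrocardiograms (ECG", without a rule for rounding or repeat readings. Statistical analysis states that "The sample size was not calculated because it was a pilot study" and plans chi-square or Fisher's exact tests and Student t-tests. It defines no per-protocol set and no subgroup or stratum based on resting heart rate.

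**The concern.** The two signs cannot both be meant as printed. If exclusions override, the equality in the inclusion criterion does nothing and the effective entry rule is strictly above 70 bpm. If the inclusion criterion is taken at its word, the equality in the exclusion criterion does nothing. The sentence in Study design and Treatment, read literally, leans towards the inclusion list because it is the only one named.

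Resting heart rate is also no side issue here. Lowering it is the rationale for the drug, heart rate is a factor in the double and triple products, and resting heart rate enters the chronotropic reserve formula. If readings are recorded in whole beats per minute, 70 is an attainable value right at the entry threshold. A reader could therefore be unsure whether such patients were enrolled, and could ask whether they were handled consistently.

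**Working it through.** **1. Where the criteria conflict.** The inputs are the two inequalities in Study Population.

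| Resting HR (bpm) | Meets inclusion (70 or more) | Meets exclusion (70 or less) | Result |
|---|---|---|---|
| 68, 69, 69.5 | no | yes | out under both |
| 70 | yes | yes | conflict |
| 70.4, 71, 72 | yes | no | in under both |

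The conflict is confined to one point, and no heart rate is left uncovered.

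**2. Whether the documents resolve it.** They do not do so in words. The sentence on meeting the inclusion criteria states a necessary condition and is silent on exclusions. Read as the whole rule, it would make every exclusion in the protocol inoperative, which cannot be intended. The two-list format carries its own convention: all inclusions met, no exclusion present. Under that convention 70 bpm is out.

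**3. What depends on the answer.** Consent precedes randomisation (Study Population), and only eligible, consenting patients are assigned 1:1 (Study design and Treatment). A reading applied at screening therefore acts before allocation and identically on both arms. The planned tests compare the randomised groups. None takes 70 bpm as a cut-point, and there is no per-protocol set from which a patient at 70 bpm could be dropped. The significance level of 0.05 is unaffected, and there is no sample-size calculation to revise.

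**4. How many patients.** This cannot be computed from the documents. As an illustration only, assume whole-number readings and normally distributed resting heart rate with mean μ and SD σ:

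- share of all screened patients at 70: P70 = Φ((70.5 − μ)/σ) − Φ((69.5 − μ)/σ)
- share of those at 70 or above: Pc = P70 / [1 − Φ((69.5 − μ)/σ)]

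For μ = 72 and σ = 10: P70 = Φ(−0.15) − Φ(−0.25) = 0.440 − 0.401 = 0.039, and Pc = 0.039 / 0.599 = 6.5%.

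| Assumed mean / SD | P70 | Pc |
|---|---|---|
| 66 / 7 | 4.8% | 15.7% |
| 66 / 10 | 3.7% | 10.1% |
| 72 / 7 | 5.5% | 8.5% |
| 72 / 10 | 3.9% | 6.5% |
| 78 / 7 | 3.0% | 3.3% |
| 78 / 10 | 2.9% | 3.6% |

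Between the tabulated means, P70 peaks at mean 70, SD 7: Φ(0.071) − Φ(−0.071) = 5.7%. The range for P70 is thus 2.9% to 5.7%. The 15.7% for Pc comes from one corner, where most screened patients fall below the threshold; the other rows lie between 3.3% and 10.1%. With an assumed 40 patients enrolled under the inclusive reading, the expected number at 70 bpm runs from 40 × 0.033 = 1.3 to 40 × 0.157 = 6.3. These are expectations, not limits, and the actual count could be higher or lower. Under the exclusive reading the number is 0.

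**The case for a change.** The best case for acting is that the correction costs almost nothing. It takes one strict inequality if enrolment is open, or one sentence stating the rule used if it is closed, and the resting heart rates are already on file. A convention that tells the reader which line to ignore does not make the two lines consistent, and an unwritten rule leaves room for uneven application at screening. A misread sign is not a good answer either: the text shows intact operators here and a strict inequality elsewhere (the ST-segment criterion for stopping the stress test), so nothing points to an extraction fault.

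The textual part of this stands: the lines disagree at 70 bpm, and the precedence rule is not written. The argument from uneven application is weaker. Discretion at entry could favour one arm only if staff could foresee the next assignment, and that would be a matter of allocation concealment, not of this sign. Other entry criteria, such as adequate acoustic windows, already leave more to judgement than one heart-rate value does. Low cost is also not a gain in itself. Either reading leaves the comparison, its error rate and its interpretation as they were, and a separate listing of patients at 70 bpm would inform no planned analysis.

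**Conclusion.** The inconsistency exists and is a clerical slip at a single boundary value. The usual reading of paired inclusion and exclusion lists settles it, the choice acts before randomisation, and no planned analysis, error rate or between-arm comparison turns on it. The documents do not allow the number of patients to be estimated. The illustrative share of 3.3% to 15.7% of patients at 70 bpm or above rests wholly on an assumed normal distribution (mean 66 to 78, SD 7 to 10) and whole-number recording.

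The conclusion assumes that one reading was applied consistently at screening and without knowledge of the coming assignment; nothing in the documents suggests otherwise. The two criteria could be reconciled whenever the text is next edited, and which side 70 bpm falls on is for the sponsor to say. No change to the design or analysis follows.

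### The printed chronotropic reserve formula lacks brackets around its whole denominator; applied literally it is negative at baseline and could reverse the apparent direction of a heart rate effect

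*Combined protocol and SAP*

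**What the plan says.** The only definition of chronotropic reserve closes the Bicycle Stress Test paragraph under Study design and Treatment: "Chronotropic reserve was estimated using the formula: $100 \times (\text{peak HR} - \text{resting HR}) / (220 - \text{age}) - \text{resting HR". One pair of brackets encloses the difference between peak and resting HR and another encloses 220 − age. None encloses the denominator together with the final resting HR term.

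Four other statements bear on the point.

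- Study Population includes patients with "HR \geq 70 bpm at rest" and excludes those with "HR \leq 70 bpm at rest or sick sinus syndrome". Resting HR at entry is therefore at or above 70 bpm, and the value of exactly 70 falls under both criteria. The minimum age is 18.
- The Introduction describes ivabradine as "resulting in selective HR reduction with no negative effects on blood pressure and inotropism".
- Patients have "exercise stress echocardiography at enrollment time (T1) and after 30 days of therapy (T2").
- Under Statistical analysis, "continuous variables were compared with Student t-test". Chronotropic reserve has no analysis of its own.

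Methods states the main purpose in terms of the double and triple product, and the second objective in terms of diastolic function and ventricular remodeling. Chronotropic reserve is in neither.

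**The concern.** Division precedes subtraction, so the printed line means [100 × (peak − rest)/(220 − age)] − rest. The first part is a percentage and the second is in beats per minute, so the result has no coherent unit. The factor of 100 indicates that a percentage was intended. With the outer brackets in place the result is a percentage, and it equals 100 when peak HR reaches 220 − age.

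The misplaced term is resting HR, which the study drug is expected to lower. If the printed form were used, the distortion would not cancel between a group on ivabradine and a group without it. Typed literally into software, the expression runs without an error message. At stake is the size, and possibly the direction, of any comparison of this exercise variable between arms or between T1 and T2.

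**Working it through.** **Inputs from the protocol.** The printed formula; resting HR at entry ≥ 70 bpm; age ≥ 18, so that M = 220 − age is at most 202. The protocol gives no chronotropic reserve value and no HR effect size, so there is no figure to reproduce. The patient values and HR falls below are assumptions.

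**Two readings.** With p = peak HR and r = resting HR:

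- Printed: P = 100(p − r)/M − r
- Bracketed: B = 100(p − r)/(M − r)

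**Step 1: sign at baseline.** For p ≤ M, P is at most 100(M − r)/M − r = 100 − 100r/M − r. This falls as r rises, so with r ≥ 70 it is at most 30 − 7000/M. That is positive only if M exceeds 7000/30 = 233.3, and M cannot exceed 202. At M = 202 the ceiling is 30 − 34.65 = −4.65 (age 18, rest 70, peak 202), where B = 100%. To reach zero at rest 70, peak HR would have to be 70 + 0.7M. At age 65 that is 70 + 0.7 × 155 = 178.5 bpm, against 220 − age = 155.

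**Step 2: an assumed patient aged 65, rest 75, peak 125 (M = 155).**

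- P = 100 × 50/155 − 75 = 32.3 − 75 = −42.7
- B = 100 × 50/80 = 62.5%

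If both rates fall by 10 bpm (65 and 115):

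- P = 32.3 − 65 = −32.7, a change of +10.0
- B = 100 × 50/90 = 55.6%, a change of −6.9

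**Step 3: when the signs differ.** Let resting HR fall by a and peak HR by b.

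- The change in P is a + 100(a − b)/M. It is positive when b/a < 1 + M/100.
- B falls when (p − r + a − b)(M − r) < (p − r)(M − r + a), which reduces to b/a > (M − p)/(M − r).

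The two forms therefore move in opposite directions when b/a lies between (M − p)/(M − r) and 1 + M/100. For the patient in Step 2 the limits are 30/80 = 0.375 and 1 + 1.55 = 2.55.

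For the same patient, with resting HR falling by 10 bpm:

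| Fall in peak HR (bpm) | Change in P | Change in B | Direction |
|---|---|---|---|
| 0 | +16.5 | +4.2 | same |
| 3 | +14.5 | +0.8 | same |
| 5 | +13.2 | −1.4 | opposite |
| 10 | +10.0 | −6.9 | opposite |
| 20 | +3.5 | −18.1 | opposite |
| 30 | −2.9 | −29.2 | same |

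Here the change in P is 10 + 100(10 − b)/155, and the change in B is 100(60 − b)/90 − 62.5.

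**Step 4: other assumed patients.** The range of b/a for opposite signs is 0.40 to 2.65 at age 55, rest 78, peak 130 (35/87 and 1 + 1.65). It is 0.48 to 2.45 at age 75, rest 72, peak 110 (35/73 and 1 + 1.45). Equal falls at rest and peak (b/a = 1) lie inside every one of these ranges.

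**The case against.** The strongest objection is that nothing shows the printed form was ever calculated. The documents report no chronotropic reserve value and say only that parameters were calculated off-line and entered in a register. A percentage of about −43 would probably be noticed. The likeliest explanation is a bracket missing from the text. This stands, and it limits the request to a correction and a confirmation.

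The bracket may also have been lost when the PDF was read, since a stacked fraction needs no outer brackets and flattening it would produce this line. The slash and the two surviving pairs of brackets point towards an inline formula in the source, but they do not settle it. The source page has to be checked.

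The consequence is also limited. The variable belongs to neither stated objective, only the generic t-test would cover it, and no eligibility or stopping rule in the protocol uses it.

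A reader might infer three stronger things that the documents do not support.

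- **That each beat of resting HR lowering adds one point whatever happens on exercise.** The change is a + 100(a − b)/M, so peak HR matters. At M = 155 the gain is about 1.65 points per beat with peak unchanged, and 1.0 only when a = b.
- **That the printed index mostly restates resting HR.** This depends on the spread of the two rates, which is not given. With assumed SDs of 8 bpm at rest and 18 bpm at peak, the terms contribute 1.645 × 8 ≈ 13 and 0.645 × 18 ≈ 12 points, which is comparable.
- **That the ivabradine effect is reversed.** That needs b/a inside the range in Step 3, and the documents give neither fall.

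**Conclusion.** The formula is wrong as written. Followed literally, it gives a negative T1 value for every eligible patient whose peak HR does not exceed 220 − age, and this follows from the protocol's own limits on age and resting HR. It can also show a gain where the bracketed form shows a loss. In the assumed patient aged 65 with HR 75 and 125, this happens when the fall in peak HR is between 0.375 and 2.55 times the fall in resting HR. Reversal is possible but not established, because it rests on HR falls that the documents do not state.

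This is probably a notation slip in an ancillary exercise variable. It does not touch the double product, the triple product or the second objective, and it is no evidence that any calculated result is wrong. It still merits correction, because this line is the variable's only specification.

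**What to change.** - Check the source page for a bracket lost in PDF reading.
- State the formula as: chronotropic reserve (%) = 100 × (peak HR − resting HR) / [(220 − age) − resting HR], with resting HR taken from the same visit as peak HR.
- Confirm from the calculation file which form was used for the values in the register.
- If the bracketed form was used, correct the text only. If the printed form was used, recompute the T1 and T2 values from the recorded heart rates and repeat any comparison that used them.

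The cost is one line of text and one check, plus, at most, a recalculation from data already held. No new measurement is needed.
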